3.3 Study Treatment Assignments and Dosages

Approximately thirty-six (36) subjects (including six actively treated lead-in participants and up to thirty-one randomized clinical trial participants) will be enrolled. The six subjects participating in the open-label lead-in will receive allo-MSC as described below in Group A. The remaining subjects will be randomized 1:1 to one of two treatment strategies:

- Group A – Receive allo-MSCs: 20 endomyocardial injections of 5 million cells each (for a total of 100 million allo-MSCs); with each injection administered in a volume of 0.4ml

IRB NUMBER: HSC-SPH-15-0443
UTHealth IRB APPROVAL DATE: 10/19/2018
The University of Texas
Health Science Center at Houston

CONFIDENTIAL AND PROPRIETARY

- Group B – Receive placebo: 20 endomyocardial injections of cell-free Buminate solution; with each injection administered in a volume of 0.4 ml.

The study product for Group A will be supplied from an allogeneic human MSC source (Appendix A); cells will be isolated from bone marrow of normal human donors and manufactured at a CCTRN cell manufacturing facility (CMF). Administering 20 injections of 0.4 ml each provides 8.0 ml of total study product volume with a cell concentration of 12.5 million total cells per ml, or 5 million cells per injection site. Twenty injections will be performed to treat the entire left ventricle (see section 5.4).

3.4 Study Endpoints

3.4.1 Safety Assessment

To demonstrate the relative safety of allo-MSCs when compared with placebo, the following safety data will be collected and analyzed by therapy group between baseline and a) 6 months and b) 12 months:

1. Major adverse cardiac events (MACE) including death, hospitalization for worsening heart failure (HF), and/or exacerbation of HF (non-hospitalization)
2. Other significant clinical events including non-fatal stroke, non-fatal myocardial infarction, coronary artery revascularization, ventricular tachycardia/fibrillation, pericardial tamponade, infectious myocarditis, hypersensitivity reaction, neoplasm, or any other potential deleterious late effects detected and corroborated by clinical presentation, laboratory investigations, image analysis, and when necessary with biopsy from suspected target sites in the body
3. All adverse events (AEs) at least grade 2 in severity (see section 7.3.1)

3.4.2 Feasibility Measures

To assess the practicality of study procedures, the following measures will be reported.

The number and percent of subjects who:

1. Have events between randomization and SPI that preclude the subjects from getting SPI
2. Receive less than 20 injections during the SPI procedure
3. Do not receive the intended dose of cells (100 million), reason, and actual dose delivered
4. Have at least one cardiac MRI endpoint measure that is uninterpretable due to issues related to the device, including, but not limited to, inability to undergo the procedure
5. Fail to complete follow-up

3.4.3 Prospectively Declared Efficacy Endpoint Measures:

To explore whether allo-MSCs produce a trend toward improved LV function and functional status when compared with placebo, the following domains¹¹¹ and measures will be evaluated:

- Myocardial evaluations by cMRI over time:
 - Function:
 - Change in LVEF
 - Change in global and regional strain (HARP MRI)
 - Structure:
 - Change in LVEDVI
 - Change in LVESVI
 - Change in LV Sphericity Index
 - Morphology:
 - Change in area of injury (e.g., inflammation, edema, fibrosis)
- Functional capacity over time:

CONFIDENTIAL AND PROPRIETARY

- Change in exercise tolerance (6MWT)
- Change in MLHF Questionnaire (subject reported)
- Clinical outcomes over time:
 - MACE
 - Cumulative days alive and out of hospital
- Biomarkers over time:
 - Change in NT-proBNP

The comparisons above will be made between the allo-*MSC* and placebo groups.

3.4.4 Sub-study Analysis:

Change in global diffuse fibrosis will be evaluated as a sub-study. This experimental endpoint will only be performed at clinical sites that have the necessary sequencing software and are qualified to participate in this sub-study by the MRI core lab.

3.5 Sample Size

This phase I study will recruit approximately 36 subjects who will have baseline and follow-up assessments to assess the changes over time in LV function and functional status. It is hoped that we will establish the precision of these estimates ¹¹¹. These measures will then be used to adequately power subsequent studies that will be able to determine the effect of therapy with statistical regularity and precision. The following measures will be assessed:

1. LV End Diastolic Volume (LVEDV) Index
2. LV End Systolic Volume (LVESV) Index
3. LV Ejection Fraction (LVEF)
4. Area of Injury (e.g., inflammation, edema, fibrosis)
5. Sphericity Index criteria
6. MLHF Questionnaire
7. Exercise tolerance (6MWT)
8. Global and regional strain

This study will recruit 31 patients with the addition of 6 patients to account for loss-to-follow-up. Subjects will be followed for one year; this is six months more than our FOCUS study which experienced a 10% follow-up loss rate. Increasing the estimation for loss-to-follow-up in SENECA to 15% over the 12 month course of follow-up would produce 4.5 patients potentially lost, administratively rounded up to 6 patients.

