Subject Population: Subjects with AIC and who are eligible to undergo cardiac catheterization/NOGA.	

Design and Investigational Plan: Approximately thirty-six (36) subjects (including six actively treated lead-in participants and up to thirty-one randomized clinical trial participants) will be enrolled. The six subjects participating in the open-label lead-in will receive allo-MSC as described below in Group A. The remaining approximately subjects will be randomized 1:1 to one of two treatment strategies:
 
 ○ Group A (15 subjects): 100×10^6 (100 million) allo-MSCs delivered in twenty 0.4 ml injections. ○ Group B (15 subjects): 20 injections of 0.4 ml cell-free Buminate solution. • For patients randomized to Group A, the allo-MSCs will be derived from allogeneic bone marrow isolated from normal, healthy donors by standard iliac crest aspiration. • Cells or placebo will be administered via the NOGA Myostar injection system. • The injections will be administered transendocardially during cardiac catheterization using the NOGA Myostar Injection System. Injections will be targeted throughout the left ventricle based on NOGA mapping and assessment of scar / fibrosis. • All consented and eligible subjects will have study product injection within 45 days of signing informed consent. • Following cardiac catheterization and allo-MSC or placebo injections, subjects will be followed at day 1, week 1, and months 1, 6, and 12 to complete all safety and efficacy assessments. 	

Eligibility Criteria:
 
Inclusion Criteria
 
To participate, a subject MUST:
 
 1. Be ≥ 18 and < 80 years of age 2. Be a cancer survivor with diagnosis of AIC 3. Have an LVEF $\leq 45\%$ by cMRI 4. Be in NYHA class II-III 5. Have received the initial diagnosis of AIC at least six months earlier and be on stable, optimally-tolerated therapy with beta-blockers, ACE inhibitors/ARBs, and/or aldosterone antagonists for 3 months, unless contraindicated 6. Have a period of at least two years of clinical cancer-free state* and low likelihood of recurrence (a five-year risk of recurrence estimated at 30% or less), as determined by an oncologist, based on tumor type, response to therapy, and negative metastatic work-up at the time of diagnosis *exceptions to this are carcinoma in situ or fully resected basal and squamous cell cancer of the skin. 7. Be a candidate for cardiac catheterization 	

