3.2 Study Design

This study will evaluate approximately thirty-six subjects. The first six subjects will receive allo-MSC therapy (open label) and will be assessed for safety and feasibility of the study procedures. Following 1 month data review of each of the six subjects by the NHLBI Gene and Cell Therapy Data and Safety Monitoring Board; this will be followed by a randomized, double-blind clinical trial enrolling approximately thirty subjects (see Section 7.7). These subjects will be randomized 1:1 to receive allo-MSCs or placebo. All subjects will undergo cardiac catheterization and study product administration using the NOGA Myostar catheter injection system. Subjects will be followed at 1 day, 1 week, 1 month, 6 months, and 12 months post study product injection. All endpoints will be assessed at the 6 and 12 month visits which will occur 180 ± 30 days and 365 ± 30 days, respectively, after the day of study product injection (Day 0).

For the purpose of the safety evaluations and endpoint analysis, we will utilize an “intention-to-treat” study population. In addition, because this phase I study is the first cell therapy study in this population, at 12 months all available standard-of-care medical records for cancer surveillance will be reviewed for cancer recurrence. Approximately thirty-six subjects will be enrolled over a 12-18 month accrual period.

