5.2 Placebo Group

Subjects randomized to the placebo group will undergo the same baseline testing and imaging as those in the allo-MSC group. The placebo will be kept on site at the local CPLs. The fifteen

CONFIDENTIAL AND PROPRIETARY

patients in the placebo group will receive transendocardial injections of cell-free Buminate solution in 20 injection sites. The placebo product will undergo QC testing before injection as indicated in Table 2b.

Table 2b. Testing of Placebo for Injection

Assay	Test Method	Specification
Rapid Sterility*	Gram Stain	No organisms
Endotoxin*	EndoSafe PTS	< 5EU/kg**
Aerobic, Anaerobic, and Fungal	14 day Bactec/BacT/ALERT assay or equivalent	No Growth

* Tests done for release criteria specification prior to injection

** Based on recipient weight and product volume

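### Section 3.5 presents six extra patients as cover for loss to follow-up, but elsewhere the same total of about 36 is made up with six open-label lead-in subjects, so the randomised cohort has at most one subject in reserve

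*Combined protocol and SAP*

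**What the plan says.** Section 3.5 opens with the overall size: "This phase I study will recruit approximately 36 subjects who will have baseline and follow-up assessments". Its last paragraph then explains how the number was reached: "This study will recruit 31 patients with the addition of 6 patients to account for loss-to-follow-up". The six are justified by a 15% loss over 12 months, raised from the 10% seen in an earlier six-month study, which "would produce 4.5 patients potentially lost, administratively rounded up to 6 patients".

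Other sections account for the same total in another way.

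- Executive Summary, on the lead-in: "The six subjects participating in the open-label lead-in will receive allo-MSC as described below in Group A". It lists 15 subjects in each randomised group, with Group B given as "15 subjects): 20 injections of 0.4 ml cell-free Buminate solution".
- Section 3.2, after the lead-in review: "this will be followed by a randomized, double-blind clinical trial enrolling approximately thirty subjects".
- Section 3.3, on the make-up of approximately 36: "including six actively treated lead-in participants and up to thirty-one randomized clinical trial participants".
- Section 5.2 also puts the placebo group at fifteen: these fifteen "patients in the placebo group will receive transendocardial injections of cell-free Buminate solution in 20 injection sites".
- Section 7.7 has the DSMB review one-month data on the six lead-in subjects before the remaining approximately thirty are recruited.
- Section 8.3.2 analyses two cohorts: the randomised subjects alone, and the randomised subjects plus the six lead-in subjects.

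**The concern.** The figures 31 and 6 appear in both accounts, but the six are a loss allowance in 3.5 and a non-randomised, all-active lead-in everywhere else. Section 3.5 does not mention the lead-in. Six subjects who all receive cells, open label, cannot replace a lost placebo subject or anyone lost from the randomised comparison.

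Section 3.5 is the plan's only sample-size justification, and its stated purpose is to learn how precise the estimates of change are so that later trials can be powered. The between-arm comparison in 8.3.2.3 asks whether treatment alters the course of each endpoint. Someone reading 3.5 alone (a DSMB member, an IRB, the planner of the next trial) would take about 31 as the number protected against loss. In the randomised cohort it is the number before any loss.

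**Working it through.** **Inputs.** Loss 15% over 12 months, 4.5 expected lost, 31 + 6 (section 3.5). Lead-in 6 (sections 3.2, 3.3, 7.7). Randomised about 30 (3.2, 7.7), up to 31 (3.3 and Executive Summary). 15 per group (Executive Summary; 5.2 for placebo). The plan gives no alpha, power, effect size or SD for the sample size, so only the counts and the loss arithmetic can be checked, and precision is expressed in units of the SD of change.

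**1. The plan's own figure.** 0.15 × 30 = 4.5, exactly as stated. The base is therefore 30, the randomised number: 0.15 × 31 = 4.65 and 0.15 × 36 = 5.4. Inflating properly, 30/0.85 = 35.3, so 36; 31/0.85 = 36.5, so 37. Taken alone, an allowance of six on a base of 30 or 31 is sound.

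**2. The two accounts of the total.**

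| Account | Sum | Total |
|---|---|---|
| 3.5: base plus loss allowance | 31 + 6 (or 30 + 6) | 37 (36) |
| 3.2, 3.3, 7.7: lead-in plus randomised | 6 + 30 to 6 + 31 | 36 to 37 |
| Both roles filled by different people | 30 + 6 + 6 to 31 + 6 + 6 | 42 to 43 |

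The third row is ruled out by the total of approximately 36 and by the ceiling of 31 randomised in 3.3.

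**3. Reserve in the randomised cohort.** Against the base of 30 (15 per group), randomising 31 leaves 31 − 30 = 1. Against the 31 written in 3.5, the reserve is 0. If losses are independent, the probability of two or more losses among 31 is 0.96 at 15% and 0.83 at 10%.

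**4. Expected 12-month completers.** 30 × 0.85 = 25.5; 31 × 0.85 = 26.35; about 13 per arm.

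**5. Precision among completers.** 95% half-width for a between-arm difference in mean change = t(0.975, n1 + n2 − 2) × √(1/n1 + 1/n2), in SD of change, with fractional expected numbers used directly:

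| Situation | n1 + n2 | Half-width (SD) |
|---|---|---|
| 30 randomised, no loss | 15 + 15 | 2.048 × 0.365 = 0.748 |
| 30 randomised, 15% loss | 12.75 + 12.75 | 2.066 × 0.396 = 0.818 |
| 31 randomised, no loss | 16 + 15 | 2.045 × 0.359 = 0.735 |
| 31 randomised, 15% loss | 13.6 + 12.75 | 2.062 × 0.390 = 0.804 |
| 36 randomised, 15% loss | 15.3 + 15.3 | 2.046 × 0.362 = 0.740 |

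Loss against no loss: 0.818/0.748 = 1.094 and 0.804/0.735 = 1.094, about 9% wider in each case. Compared with a trial that did randomise 36, the plan with 30 randomised is about 11% wider (0.818/0.740 = 1.106) and with 31 randomised about 9% wider (0.804/0.740 = 1.087).

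**The case against.** The best defence is that 3.5 counts the whole study. It speaks of about 36 subjects with baseline and follow-up assessments, the lead-in subjects go through the same screening and baseline procedures (section 4.2), and 8.3.2 runs every analysis on the total cohort as well. On that basis 36 × 0.85 = 30.6 and 37 × 0.85 = 31.45 completers, close to the 31 in 3.5, and 3.5 never says that the allowance protects the randomised cohort or an arm. This does not rescue the text. The 4.5 losses are 15% of 30, not of 36; the extra six are all active and non-randomised; and 8.3.2 also analyses the randomised cohort alone, where they do not count.

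Other points stand in part:

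- That the six in 3.5 are the lead-in is an inference, since 3.5 does not name them. The contradiction between sections is not an inference.
- The loss arithmetic in 3.5 is correct taken alone; the fault is in what the six are said to be.
- The 9% compares loss with no loss. Other comparators give 7.5% (0.804/0.748, for 31 randomised against 30 completers) to about 11%. The order of size is the same.
- The mixed model listed first in 8.3.2.3 uses month-6 data from subjects lost later, so a completer calculation overstates the loss of precision for that model. The Wilcoxon comparisons of change to 12 months get no such help.
- Fifteen per group is nominal: a 1:1 split of 31 cannot be 15 and 15.
- The consequences are limited. Safety and feasibility are primary, failure to complete follow-up is itself a feasibility measure, and 8.6 calls the results preliminary.

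**Conclusion.** The concern holds. Section 3.5 claims a loss allowance that the randomised design described in the rest of the protocol does not have. The randomised cohort has a reserve of at most one subject, measured against a base of 30, for 4.5 expected losses. About 25 to 26 randomised subjects are expected to complete 12 months, where 36 to 37 would have to be randomised to keep 30 to 31.

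The cost in precision is about 9% on the completer half-width (0.748 to 0.818 SD for 30 randomised, 0.735 to 0.804 SD for 31). For the planned mixed model this is roughly an upper bound on the effect of loss. It assumes equal loss and equal SD of change in the two arms. No power or precision target is breached, because none is stated. The matter should be corrected because 3.5 is wrong as written and its figures are meant to inform later trials; it does not threaten the primary aims.

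**What to change.** Rewrite the last paragraph of 3.5 to agree with 3.2, 3.3 and 7.7. Remove the sentence on 31 plus 6 patients and the closing phrase that rounds 4.5 up to 6, and keep the 10% loss in the earlier study as the basis for 15%. Suggested wording:

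> Approximately 36 subjects are enrolled: six open-label lead-in subjects, all receiving allo-MSCs, who are used for the DSMB lead-in review (7.7) and, among the outcome analyses, only in the total cohort (8.3.2); and about 30 (up to 31) subjects randomised 1:1. No additional subjects are randomised to offset loss to follow-up. With 15% loss at 12 months (about 4.5 of 30), about 25 to 26 randomised subjects (about 13 per arm) are expected to complete 12 months, giving an approximate 95% CI half-width of 0.80 to 0.82 SD for a between-arm difference in mean change among completers.

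This changes wording only; enrolment, design and analysis stay as they are. The cost is a less favourable stated number of completers and precision. The sponsor should confirm the intention first. If a separate reserve of randomised subjects was meant, 3.5 should say so, and the Executive Summary, 3.2, 3.3 and 7.7 would have to change instead, to a total of 42 to 43, along with the fifteen in 5.2.

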4.0 IDENTIFICATION AND ENROLLMENT OF SUBJECTS

Potential subjects will be identified by the study team and medical records will be reviewed for possible consent to the study.

4.1 Recruitment and Screening (prior to consent)

The study Sponsor (Data Coordinating Center) will provide participating clinical centers with a variety of materials to aide in recruitment. This may include, but is not limited to, informational DVDs and brochures which provide education about heart failure and include information about the study; physician referral letter templates which can be used to promote awareness of the study in the cardiovascular community; templates for flyers which can be utilized at approved clinic locations and as part of health fair materials; templates for print advertisements which can be utilized in newsprint and media campaigns; Research Match     

CONFIDENTIAL AND PROPRIETARY

registry, may also be utilized to identify potential candidates for trial participation. Not all materials have been developed prior to trial initiation; however, each of these methods (the templates, final products, and services) will be reviewed and approved by both the Sponsor IRB and the clinical center IRB prior to use.

Screening subjects includes reviewing medical records for inclusion/exclusions prior to consent, as well as subjects' imaging studies. Subjects who are determined to have a diagnosis of AIC, have NYHA class of II or higher, have LVEF \leq 45% by cMRI, and are a candidate for cardiac catheterization, and do not have evidence in their medical record of study exclusions, should be approached about consenting to the study. EF \leq 45% can be defined by gated blood pool scan (MUGA), cMRI, left ventriculogram, or EF \leq 40% by two-dimensional echocardiogram.

In order to exclude those with ischemic heart disease, available imaging in the patient's chart will be reviewed. Acceptable imaging for the detection of obstructive CAD includes coronary arteriogram or any non-invasive test within five years prior to enrollment in the study provided that there have been no symptoms or evidence of CAD since the test. If the subject has not had one of these tests done in the corresponding timeframe, then the individual should have one of these tests as standard of care (institutional choice) to be reviewed for entry into the study. If a test is not otherwise authorized under a patient's insurance under standard of care, a stress echo will be included as part of the baseline testing and paid for by the study, to be reviewed for eligibility.

Prior to study entry an oncological assessment form will be completed by the subject's oncologist to assess the risk of cancer recurrence. Current medical records will be reviewed to verify the absence of any new metastatic disease, stage 4, or recurrence.

4.2 Consent

Before being admitted to the clinical study, all subjects must consent in writing to participate. An informed consent form (ICF) will be given to each subject which will contain all United States federally required elements, all International Conference of Harmonisation of Technical Requirements for Registration of Pharmaceuticals for Human Use (ICH)-required elements, and Health Insurance Portability and Accountability Act Authorization (HIPAA) information in language that is understandable to the subject.

A separate consent form will be utilized for six subjects participating in the open-label lead-in. These subjects will undergo the same screening and baseline procedures as those who will participate in the randomized phase of the study (see Section 6.0 below); however, all lead-in subjects will receive the allo-MSC product.

Potential participants will be approached by one of the study investigators or research coordinators. Information regarding study participation will be provided to the potential participant. The informed consent includes descriptions of all study related procedures, all possible risks to participant, and the time commitment involved with participating. The ICF and review must be in a form understandable to the subject. The Investigator or designee and the subject must both sign and date the ICF after review and before the subject can participate in the study. The subject will receive a copy of the signed and dated form, and the original will be retained in the site study files. The Investigator or his/her designee must emphasize to the subject that study participation is entirely voluntary and that consent regarding study participation may be withdrawn at any time without penalty or loss of benefits to which the subject is otherwise entitled.

All consent forms will have IRB approval. Individuals who agree to participate will receive a copy of the signed informed consent. The research staff member will receive a copy of the signed informed consent will

4.3 Inclusion Criteria

To participate, a subject **MUST**:

1. Be ≥ 18 and < 80 years of age
2. Be a cancer survivor with diagnosis of AIC
3. Have an LVEF $\leq 45\%$ by cMRI
4. Be in NYHA class II-III
5. Have received the initial diagnosis of AIC at least six months earlier and be on stable, optimally-tolerated therapy with beta-blockers, ACE inhibitors/ARBs, and/or aldosterone antagonists for 3 months, unless contraindicated
6. Have a period of at least two years of clinical cancer-free state* and low likelihood of recurrence (a five-year risk of recurrence estimated at 30% or less), as determined by an oncologist, based on tumor type, response to therapy, and negative metastatic work-up at the time of diagnosis
7. Be a candidate for cardiac catheterization

